has been reported to improve gastrointestinal disorders, including abdominal pain (22), constipation (23) and functional dyspepsia (24), but there is no study on ta VNS in the treatment of IBS-C. Based on the integrative effects of taVNS on both pain and motility we observed in the animal model of functional dyspepsia and patients with abdominal pain-related functional gastrointestinal disorders (22, 24, 25), we hypothesized that taVNS might improve symptoms in patient with IBS-C by enhancing vagal efferent activity. The aim of this study is to investigate the effects and mechanisms of taVNS on symptoms in patients with IBS-C.

Methods

Study design and plan

(1) The patients diagnosed with IBS-C are screened and the sample size is estimated;

(2) The inclusion and exclusion criteria are selected and informed consent is signed;

(3) The treatment group is treated with taVNS, while the control group is treated with sham taVNS. The blood samples are collected and outcome measures are taken;

(4) Samples are sent for inspection and the results are statistically analyzed.

Patients

Inclusion criteria:

1) age 18–75 years,

2) willing to sign a written informed consent form,

3) met the Rome IV diagnostic criteria (26) for IBS-C.

Exclusion criteria:

1) had a history of previous abdominal surgery (other than appendectomy),

2) suffering from carcinoma,

3) had any organic diseases causing constipation or neurologic diseases such as multiple sclerosis, rachischisis, Parkinson's disease or spinal cord injury,

4) taking antidepressant agents including tricyclic antidepressants and selective serotonin reuptake inhibitors,

5) had a serious concomitant disease of the heart, liver, kidney, or diabetes,

6) women during pregnancy or lactation,

7) participating in another trial or enrolled in a trial during the past month,

8) allergic to surface electrodes.

Withdrawal criteria:

1) The subject or his legal guardian voluntarily requests to withdraw;

- 2) Violation of inclusion / exclusion criteria;
- 3) Withdraw when other unexplained serious complications occur;
- 4) If pregnancy occurs during treatment, withdraw from the study;

5) For safety reasons, the study sponsor proposed to stop the study;

6) Subjects whose ethics committee decided to stop the study;

7) Subjects who are considered unsuitable for further study.

The reason and date of withdrawal are recorded, and the withdrawal rate is counted at the end of the study.

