The subjects who withdraw from the study will take appropriate treatment measures according to the judgment of the researchers.

Trial interventions

Enrolled patients will be randomized to undergo either taVNS or sham-taVNS. The taVNS treatment is performed at auricular cymba concha, while Sham-taVNS is performed at a sham point (elbow area). **Study Design and Protocol**

Enrolled patients are randomly divided into two groups (taVNS and sham-taVNS) with a ratio of 1:1 according to a computer-generated random digital table. The sample size is calculated by G*power analyses based on our preliminary study. One week before the start of the study, patients are asked to stop all constipation and IBS medications, including laxatives, prokinetic agents, probiotics, and antispasmodics. After one-week run-in period, patients in each group are requested to complete the following questionnaires once a week: the visual analog scale (VAS) for abdominal pain, IBS symptom severity score (IBS-SSS) for the overall IBS symptoms, IBS quality of life questionnaire (IBS-QOL) for patient's quality of life, Bristol Stool Form Scale (BSFS) for the stool type, Self-Rating Anxiety Scale (SAS) for anxiety, Self-Rating Depression Scale (SDS) for depression, and the bowel diary for the number of complete spontaneous bowel movements per week. Autonomic function is assessed at the baseline and after 4 weeks of treatment. by the spectral parameters of heart rate variability (HRV), calculated using spectral analysis of R-R intervals in electrocardiogram (ECG). A blood sample is taken at 8 a.m. at baseline and after 4 weeks treatment, Serum and plasma are separated and frozen at - 80 °C. The chronic taVNS and sham-taVNS intervention is performed twice a day (8am and 8pm) for half an hour each time, lasting for four weeks. During the run-in and treatment periods, only Macrogol 4000 and pinaverium are permitted for use, when the patient could not tolerate symptoms of constipation and abdominal pain. The flowchart is shown in Figure 1, and the study schedule is detailed in Table 1.

Figure 1. Flowchart of the study design.

	Baseline	Week 1	Week 2	Week 3	Week 4
Consent	×				
VAS	×	×	×	×	×
IBS-SSS, IBS-QOL	×	×	×	×	×
SAS, SDS, BSFS	×	×	×	×	×
HRV	×				×
Blood	×				×

Table 1. Study schedule. A bowel diary is recorded during the treatment.

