VAS, visual analog scale; IBS-SSS, IBS symptom severity score; IBS-QOL, IBS quality of life questionnaire; SAS, Self-rating Anxiety Scale; SDS, Self-rating Depression Scale; BSFS, Bristol stool form scale; HRV, heart rate variability.

Randomization

Enrolled patients are randomly divided into two groups (taVNS and sham-taVNS) with a ratio of 1:1 according to a computer-generated random digital table, which contains 21 odd numbers and 21 even numbers. Odd numbers represent taVNS, while even numbers represent sham-taVNS, and enter corresponding groups according to the sequence of patients.

Blinding

The patients are blinded to the type of treatment.

Serious adverse events (SAEs)

Pain at the stimulation site and allergy to the electrode are adverse events. Lowering the intensity of stimulation can relieve or eliminate pain. If the patient is allergic to the electrode, we will terminate the treatment and let the patient withdraw from the study.

Statistics

Quantitative variables are reported as means \pm standard deviations (SD), while categorical data qualitative variables are presented as absolute values and percentages. Categorical data are compared using the chi-squared test. The independent sample t-test is used to assess the difference between the sham-taVNS and taVNS groups; The paired student's t-test is applied to evaluate the differences before and after the taVNS or sham-taVNS treatment. *P*<0.05 is considered statistically significant.

Sample size estimation

G-Power software is used for calculation, and the steps are as follows:

- 1. T test, mean difference between two dependent means (two groups)
- 2. A priori: compute required sample size, given α , power, and effect size
- 3. Tails: One
- 4. Effect size: In the previous study, the number of spontaneous defecation was: 2.3 ± 2.1 (SD) in sham stimulation group; 3.7 ± 1.4 (SD) in true stimulation group. Therefore, the effect size dz=0.784.
- 5. $\alpha = 0.05$; $\beta = 0.2$, $1 \beta = 0.8$;

Based on the above data, G-Power software calculated total sample size: n = 42

Ethics committee review

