The protocol, written informed consent, and information directly related to the subjects will be submitted to the Ethics Committee for written approval before the study can be formally carried out. The researcher must submit an annual report of the study to the ethics committee at least annually (if applicable). When the study is terminated and / or completed, the researcher must inform the ethics committee in writing; the researcher must timely report to the ethics committee all changes in the research work (such as the revision of protocol and / or informed consent number), and shall not implement these changes without the approval of the ethics committee, unless it is made to eliminate obvious and direct risks to the subjects Changes to the contract. When this happens, the ethics committee will be informed.

Informed consent

The researcher must provide the subject or his legal representative with the informed consent which is easy to understand and approved by the ethics committee, and give the subject or his legal representative sufficient time to consider the study. The subject shall not be enrolled until the written informed consent is obtained from the subject. All updated versions of informed consent and written information will be provided to the subjects during their participation. Informed consent should be kept as an important document of clinical trials for future reference.

Confidentiality measures

Subject's medical records (research medical records, examination reports, etc.) will be kept in the hospital, and the doctor will record the examination results in outpatient medical records. Researchers, sponsor representatives and ethics committee will be allowed to access subject's medical records. Any public report on the results of this study will not disclose subject's personal identity. We will make every effort to protect the privacy of subject's personal medical data within the scope permitted by law. Subject's medical records will not be used for any purposes other than this study.

Timeline

1) July 2019 - August 2019: Screen and confirm the clinical diagnosis of IBS-C patients, and estimate the sample content

2) September 2019–July 2020: Patient recruitment, and for the selected participants, signed an informed consent form, underwent percutaneous auricular vagus nerve stimulation treatment, and collected the outcome measures

3) August 2020-October 2020: Data analysis

References

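### Electrode allergy, an unexplained serious complication or pregnancy ends study participation, with no further outcome assessment and no record of how the event ended planned

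*Combined protocol and SAP*

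**What the plan says.** Three events lead out of the study.

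- **Electrode allergy** (Serious adverse events): "If the patient is allergic to the electrode, we will terminate the treatment and let the patient withdraw from the study".
- **Serious complications** (Withdrawal criteria, item 3): "Withdraw when other unexplained serious complications occur".
- **Pregnancy** (Withdrawal criteria, item 4): "If pregnancy occurs during treatment, withdraw from the study".

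The data rule for withdrawals comes straight after the list: "The reason and date of withdrawal are recorded, and the withdrawal rate is counted at the end of the study". The next sentence deals with care: "The subjects who withdraw from the study will take appropriate treatment measures according to the judgment of the researchers".

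Table 1 schedules the questionnaires at baseline and Weeks 1 to 4. Heart rate variability (HRV) and blood are scheduled at baseline and Week 4 only. The note to the table ties the bowel diary to the treatment period. There is no adverse-event row. The Statistics section describes no safety analysis, no handling of missing data and no rule for analysing patients who leave early.

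**The concern.** Ending an intervention and ending observation are different decisions, and the allergy sentence takes both at once. Two kinds of information then fall away.

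- **The event.** The withdrawal reason shows that it happened. Nothing in the plan calls for its duration, resolution or relation to the device to be recorded, or for the outcome of a pregnancy.
- **The efficacy and mechanism outcomes.** The remaining weekly questionnaires and the Week 4 HRV and blood samples are not collected, so the missing data are related to harm. The electrodes sit at different sites in the two arms (ear and elbow), so this loss could differ by arm. That is a possibility; the documents give no rates.

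The background states that taVNS has not been studied in IBS-C. In a first trial with 21 patients per arm, the course of each such event is worth having, and each lost patient counts.

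**Working it through.** **1. The passages side by side**

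| Event | Stated consequence | Data stated | Follow-up or outcome of event stated |
|---|---|---|---|
| Electrode allergy | Treatment ends and patient leaves study | Reason and date | None |
| Unexplained serious complication | Withdrawal | Reason and date | None |
| Pregnancy during treatment | Withdrawal from study | Reason and date | None |
| Stimulation-site pain | Intensity lowered; no withdrawal stated | None stated | None |

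The allergy sentence names two separate acts, so it cannot be read as stopping treatment alone. Item 3 does not say what is withdrawn from. It stands in the study's withdrawal list, though, and the care sentence that follows speaks of leaving the study.

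**2. Assessments lost.** From Table 1 there are 4 post-baseline questionnaire assessments and 1 post-baseline HRV and blood assessment. A patient withdrawn after the assessment of week *w* loses (4 − *w*) of 4 questionnaire assessments. The timing is an assumption, so the full range is shown.

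| Withdrawn after | Questionnaire assessments lost | Post-baseline HRV and blood lost |
|---|---|---|
| Baseline | 4 of 4 | 1 of 1 |
| Week 1 | 3 of 4 | 1 of 1 |
| Week 2 | 2 of 4 | 1 of 1 |
| Week 3 | 1 of 4 | 1 of 1 |

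Any such withdrawal before the Week 4 visit removes all post-baseline HRV and blood data for that patient. The patient then drops out of the paired before-after t-test for those measures.

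**3. Share of an arm.** Randomization gives 21 per arm. One patient is 1/21 = 4.8%, two are 2/21 = 9.5% and three are 3/21 = 14.3%.

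**4. Scale against the planned power.** Sample size estimation gives means 2.3 (SD 2.1) and 3.7 (SD 1.4), one-sided α = 0.05 and power 0.80.

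- Pooled SD = √[(2.1² + 1.4²)/2] = √3.185 = 1.785.
- Effect size = (3.7 − 2.3)/1.785 = 0.784, as stated.
- Power for two independent groups of *n*, from the noncentral t distribution with 2*n* − 2 degrees of freedom and noncentrality 0.784 × √(*n*/2): *n* = 21 gives 0.803. The stated total of 42 is therefore reproduced. (The plan labels the test as one for dependent means, which would give 12; that is a separate matter.)
- If 1, 2 or 3 patients per arm were lost from the analysis, power would be 0.785, 0.766 or 0.745. These losses are assumed for scale only; the plan states no withdrawal rate and makes no allowance for one.

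**The case against.** **Not every harm is affected.** A reader might infer that each harm the plan regards as important goes unobserved. The text does not support that. The adverse-event section names two harms: "Pain at the stimulation site and allergy to the electrode are adverse events". For pain it adds: "Lowering the intensity of stimulation can relieve or eliminate pain"; no withdrawal is stated.

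**Outcomes may still be seen.** Care continues after withdrawal. Under Confidentiality measures, medical records stay in the hospital, open to researchers, and "the doctor will record the examination results in outpatient medical records". This stands against any claim that outcomes cannot be known. It does not close the gap: that section governs access and privacy, and requires neither a contact nor an outcome field in the trial data.

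**Silence is not prohibition.** The protocol says that reason and date are recorded; it does not say that nothing else is. The consent form is not in the text available, so follow-up terms there cannot be excluded. The allergy wording could also be read as permission to leave. Even so, the protocol does not say what is collected from a patient who stays.

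**The lists do not clearly conflict.** Allergy is not named among the withdrawal criteria, which a reader might call a contradiction. But allergy to surface electrodes is an exclusion criterion, and violating the entry criteria is a withdrawal criterion, so the case can be read as covered. A cross-reference is enough.

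**Consequences can be overdrawn.** A reader might infer that the trial's benefit-risk conclusion would rest on unharmed patients. No such conclusion is planned; the aim concerns effects on symptoms and mechanisms. Known electrode allergy is excluded at entry, so cases may be few. A contact with all completers after Week 4 would be a matter of preference and does not follow from the withdrawal rule.

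**Conclusion.** The point holds in a limited form. For electrode allergy, unexplained serious complications and pregnancy, the plan ends study participation. It states only reason and date, plus an overall withdrawal rate, and plans neither further outcome assessment nor a record of how the event ended.

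Per affected patient, the cost is 1 to 4 of the 4 post-baseline questionnaire assessments, depending on timing (3 of 4 if withdrawn after Week 1), and all post-baseline HRV and blood values. Each patient is 4.8% of an arm. The total effect cannot be sized, because the documents give no event rate. The sample-size arithmetic is untouched.

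This rests on taking the withdrawal wording at face value and on no follow-up terms existing outside the text. It is worth correcting because the rule itself creates avoidable missing data, and the correction is cheap.

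**What to change.** Leave unchanged the events for which stimulation stops. In the protocol text:

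1. Define stopping stimulation and withdrawing from the study as separate statuses, each with its own date and reason.
2. State that, unless they withdraw consent, patients who stop for these events continue the scheduled weekly questionnaires, including the bowel diary (now tied to the treatment period) and, where appropriate, the Week 4 HRV and blood assessments. Analyse them in their randomised arm.
3. For each such event, and for any pregnancy, record end date, outcome and relation to the device, using the hospital records where permitted.
4. Reconcile or cross-refer the withdrawal list and the allergy sentence, without adding a new trigger.

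The cost is some protocol wording, a few form fields and a small amount of site time.

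The Timeline places recruitment between September 2019 and July 2020, while the document is dated 5/25/2022. If enrolment is already complete, what remains is to retrieve event outcomes from the hospital records where permitted and to report that they were not collected prospectively.

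### One P<0.05 rule covers every between-group and within-arm test, with no primary outcome, primary visit, testing order or multiplicity control, so the plan does not say which result decides whether taVNS works

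*Combined protocol and SAP*

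**What the plan says.** The Statistics section is the whole analysis plan, and the synopsis repeats its t-tests and threshold. Apart from chi-squared tests for categorical data, it has two comparisons. Between arms: "The independent sample t-test is used to assess the difference between the sham-taVNS and taVNS groups". Within each arm: "The paired student's t-test is applied to evaluate the differences before and after the taVNS or sham-taVNS treatment". A single threshold follows: P<0.05 "is considered statistically significant". No outcome, visit or sidedness is attached to any of these tests.

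Under Study Design and Protocol, "patients in each group are requested to complete the following questionnaires once a week": pain VAS, IBS-SSS, IBS-QOL, BSFS, SAS and SDS. The same list ends with "the bowel diary for the number of complete spontaneous bowel movements per week". That makes seven weekly outcomes. HRV and blood are added at baseline and week 4, and no blood analyte is named.

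The Sample size estimation section describes its test as "T test, mean difference between two dependent means (two groups" and sets it one-tailed. It takes its effect from spontaneous defecation: "In the previous study, the number of spontaneous defecation was: 2.3 ± 2.1 (SD) in sham stimulation group", against 3.7 ± 1.4 under true stimulation. It concludes "Therefore, the effect size dz=0.784" and a total of 42, at alpha 0.05 and power 0.8. The synopsis objective names abdominal pain first, then other symptoms.

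**The concern.** A trial with several outcomes needs one stated test, or a stated rule across tests, on which the efficacy conclusion rests. This plan has neither, and the surrounding text does not supply one. The objective, the sample size and the outcome list point to three different variables: abdominal pain, a defecation count with no time unit, and complete spontaneous bowel movements per week. None is designated primary.

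Followed as written, any between-group test that falls below 0.05, on any outcome at any week, could be reported as efficacy. So could a before-after change in the taVNS arm alone. Such a change also picks up regression to the mean, placebo response and natural fluctuation, none of which separates taVNS from sham. Nor does the 80% power belong to any declared primary analysis.

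**Working it through.** **1. Reproduce the stated sample size.** Inputs from Sample size estimation: means 2.3 and 3.7, SDs 2.1 and 1.4, one-tailed alpha 0.05, power 0.80.

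- Pooled SD = √[(2.1² + 1.4²)/2] = √3.185 = 1.785.
- Effect size = (3.7 − 2.3)/1.785 = 0.784, as stated.
- Two independent groups, noncentral t, one-sided 0.05: 21 per arm gives power 0.803 and 20 per arm gives about 0.785. So N = 42 reproduces.
- The same 21 per arm, two-sided 0.05: power 0.699. Reaching 80% two-sided would take 27 per arm, 54 in total.
- A true dependent-means test at dz = 0.784, one-sided 0.05: 11 pairs gives 0.780 and 12 pairs gives 0.816, so it would need 12 pairs.

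The figure 42 therefore belongs to an independent-groups calculation, although the step is labelled as dependent means with dz.

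**2. False-positive risk across the seven weekly outcomes at one visit.** Inputs: seven outcomes (Study Design and Protocol) and threshold 0.05 (Statistics). Two inputs are not in the documents and are assumed: the correlation ρ between outcomes, taken as equal for all pairs, and the sidedness of the analysis. Outcomes are oriented so that positive means benefit, and only results favouring taVNS are counted.

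P(at least one) = 1 − ∫ φ(u) · Φ[(c − √ρ·u)/√(1 − ρ)]⁷ du, where c is the normal quantile at 0.975 (two-sided 0.05) or 0.95 (one-sided 0.05). At ρ = 0 this reduces to 1 − 0.975⁷ = 0.162 and 1 − 0.95⁷ = 0.302.

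| ρ | Two-sided 0.05 (one test: 2.5%) | One-sided 0.05 (one test: 5%) |
|---|---|---|
| 0 | 16.2% | 30.2% |
| 0.3 | 13.7% | 24.5% |
| 0.5 | 11.5% | 20.3% |
| 0.7 | 8.9% | 15.9% |
| 0.8 | 7.4% | 13.4% |
| 0.9 | 5.7% | 10.5% |

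Simulated t-tests with 21 per arm agree to within about half a percentage point. The count leaves out the other three treatment weeks, HRV, blood and all within-arm tests.

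**3. Within-arm paired test (illustration).** Suppose both arms improve equally, so there is no treatment effect. With 21 patients and two-sided 0.05, the noncentrality is dz·√21. At an assumed improvement of 0.5 SD of change this is 0.5 × 4.583 = 2.29, and the taVNS arm's paired test shows significant improvement in 59% of trials. At 0.3 and 0.8 SD the figures are 26% and 94%.

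**4. What 21 per arm can detect if pain is primary.** At 80% power: 0.89 SD two-sided or 0.78 SD one-sided.

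**The case against.** **The size depends on the assumed correlation.** This stands. A reader might infer a false-positive rate of 30%, but that needs seven uncorrelated outcomes and one-sided testing. Symptom, quality-of-life and mood scores from the same patients are unlikely to be uncorrelated, and one tail is stated only for the sample size. That is why 0.5 to 0.7 is the main range here. Even at 0.9 the risk is about twice that of a single test.

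**The within-arm figures are hypothetical.** They are, and a reader might go further and infer that the plan treats a before-after change as proof of efficacy. It does not say so, and it lists a between-group test as well. The point is only that nothing limits how the paired tests may be used.

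**The sample size shows the intended primary.** It is tempting to read the bowel count as an implicit primary carrying 80% power. The planning variable has no time unit and is not described as complete movements, whereas the diary counts complete movements per week. The documents do not show that they are the same variable, and they do not call either one primary.

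**The sample size is wrong.** A reader might infer this from the dependent-means label. The number is right for the one-sided, two-group comparison; the label is a wording error, separate from multiplicity.

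**The primary could only be chosen after the data were seen.** The document is dated May 2022 and its Timeline places analysis in August to October 2020. That is a schedule, not evidence of when the analysis was done. The plan also requires the protocol to go to the ethics committee before the study starts, so an earlier version may have named a primary. The dates call for disclosure; they do not establish post hoc selection.

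**Conclusion.** Wrong as written. The omission is a matter of text and rests on no assumption: no primary outcome, primary visit, testing order, multiplicity rule or exploratory status appears anywhere, while one P<0.05 rule covers every test.

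The size rests on equal correlation between outcomes and on sidedness, neither of which the documents give. At correlation 0.5 to 0.7, seven null between-group tests at one visit yield at least one result favouring taVNS in about 11% to 9% of trials two-sided, or 20% to 16% one-sided, against 2.5% and 5% for a single test. Over correlation 0 to 0.9 the ranges are 16% to 6% and 30% to 10%. Testing further weeks, HRV and blood in the same way would raise the chance further. The within-arm figure of 59% is an illustration that depends on the assumed 0.5 SD improvement in both arms.

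**What to change.** 1. In Statistics, name one primary outcome at week 4, compared between groups. If it is the bowel-movement count, first confirm that the planning figures (2.3 ± 2.1 and 3.7 ± 1.4) describe the same variable and time unit as the diary. If it is pain VAS, state its own power, using the detectable differences above.
2. Say whether the week-4 value or the change from baseline is tested. Study Design and Protocol lists the diary among the weekly instruments completed after the run-in, while the note to Table 1 places it during treatment. Reconcile the two on whether a pre-treatment diary week exists; a change score or paired test on bowel movements needs one.
3. Label all other outcomes and weeks, HRV and blood as secondary or exploratory with no efficacy claim, or state the multiplicity control for any that will support a claim.
4. Report within-arm paired tests as descriptive only.
5. State the sidedness of the analysis. For the bowel outcome only, and only if the planning variable is the one collected, power at 21 per arm is 0.80 one-sided or 0.70 two-sided. Correct the dependent-means and dz label to two independent groups.
6. Alternatively, declare the study exploratory and make no confirmatory claim. If the data had been analysed before the May 2022 document, disclose any primary as post hoc unless an earlier dated version named it.

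Cost: text changes only, with no added patients. Stated power for the bowel outcome falls to about 0.70 if the test is two-sided, and efficacy claims on unplanned outcomes or within-arm changes are lost. Naming one primary costs less power than adjusting all seven: Bonferroni at 0.05/7, with effect size 0.784 and 21 per arm, leaves about 0.40 two-sided or 0.50 one-sided.

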Clinical study protocol

Protocol Title: The efficacy and mechanisms of transcutaneous auricular vagus nerve stimulation on symptoms in patients with constipation-predominant irritable bowel syndrome

NCT NUMBER: NCT05392439

Document Date: 5/25/2022

Principal Investigator: [name]

Sponsor: Shanghai East Hospital, Tongji University

Title	The efficacy and mechanisms of transcutaneous auricular vagus nerve stimulation on symptoms in patients with constipation-predominant irritable bowel syndrome				
Protocol number	2020-006				
Sponsor	Shanghai Fast Hospital Tongii University				
Indication	Constinution-predominant Irritable Rowel Syndrome (IRS-C)				
Objective/Aim	This study aims to investigate the effects and possible mechanisms of				
	transcutaneous auricular vagal nerve stimulation (taVNS) on abdominal				
	pain and other symptoms in patients with IBS-C				
Sample size	N = 42				
Case selection	Inclusion criteria				
criteria	1) age $18-75$ years.				
	2) willing to sign a written informed consent form				
	3) met the Rome IV diagnostic criteria for IBS-C				
	Exclusion criteria:				
	1) had a history of previous abdominal surgery (other than appendectomy),				
	2) suffering from carcinoma,				
	3) had any organic diseases causing constipation or neurologic diseases				
	such as multiple sclerosis, rachischisis, Parkinson's disease or spinal cord				
	injury,				
	4) taking antidepressant agents including tricyclic antidepressants and				
	selective serotonin reuptake inhibitors,				
	5) had a serious concomitant disease of the heart, liver, kidney, or diabetes,				
	6) women during pregnancy or lactation,				
	7) participating in another trial or enrolled in a trial during the past month,				
	8) allergic to surface electrodes.				
Timeline	1) July 2019 - August 2019: Screen and confirm the clinical diagnosis of				
	IBS-C patients, and estimate the sample content				
	2) September 2019–July 2020: Patient recruitment, and for the selected				
	participants, signed an informed consent form, underwent percutaneous				
	auricular vagus nerve stimulation treatment, and collected outcome				
	measures				
	3) August 2020-October 2020: Data analysis				
Statistical analysis	The independent sample t-test is used to assess the difference between the				
	sham-taVNS and taVNS groups; The paired student's t-test is applied to				
	evaluate the differences before and after the taVNS or sham-taVNS				

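### The arms are compared by a t-test with no baseline covariate, although Table 1 schedules a baseline for eight outcomes; adjusting for it is a low-cost gain in precision

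*Combined protocol and SAP*

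**What the plan says.** The Statistics section, repeated in the synopsis, sets the between-arm analysis of quantitative outcomes in one sentence: "The independent sample t-test is used to assess the difference between the sham-taVNS and taVNS groups". The baseline enters only through a second test, run separately in each arm: a paired "t-test is applied to evaluate the differences before and after the taVNS or sham-taVNS treatment". No section mentions ANCOVA, a regression model, a repeated-measures model or a baseline covariate.

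Table 1 marks VAS, IBS-SSS, IBS-QOL, SAS, SDS and BSFS at baseline and at weeks 1 to 4, and HRV and blood at baseline and week 4. The Study Design and Protocol section agrees on the last two: "Autonomic function is assessed at the baseline and after 4 weeks of treatment" and "A blood sample is taken at 8 a.m. at baseline and after 4 weeks treatment".

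The bowel-movement count differs. It has no row in Table 1, whose caption says only "A bowel diary is recorded during the treatment". It is nevertheless the variable behind the sample size, which opens its effect-size step with "In the previous study, the number of spontaneous defecation was".

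**The concern.** Baseline values of symptom scores and physiological measures usually carry some information about the later values. A between-arm test that ignores them leaves that variation in the error term, and at 21 per arm there is little precision to spare. The paired tests do use the baseline, but they do not compare taVNS with sham and cannot supply the missing precision.

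The plan also leaves the form of the t-test open. It does not say which of weeks 1 to 4 is tested, or whether the test is on values or on changes from baseline. A change-score test would use the baseline, but in a fixed one-to-one way that is inefficient unless the correlation is high.

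At stake is the width of the interval for the treatment difference. Validity is not in question, and the plan states no rule that would infer efficacy from the within-arm tests.

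**Working it through.** **1. The plan's own sample size.** From Sample size estimation: 2.3 (SD 2.1) on sham, 3.7 (SD 1.4) on active stimulation, one-tailed, alpha 0.05, power 0.8, total 42.

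- Pooled SD = √((2.1² + 1.4²)/2) = √3.185 = 1.785
- d = (3.7 − 2.3)/1.785 = 0.784
- Independent groups, one-sided, noncentral t: 21 per arm, 42 in total, power 0.803. This reproduces the stated figure.
- Paired design with 0.784 as the paired effect size: 12 patients (one-sided) or 15 (two-sided). Neither is 42.

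Although the section labels the calculation as one for dependent means, 42 is reproduced only as a two-group comparison. The trial therefore appears to be sized on the between-arm contrast, the one discussed here.

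**2. Expected interval width.** This needs no effect size. Assumptions: n = 21 per arm, equal SD at both times, and baseline-to-follow-up correlation ρ of 0, 0.3, 0.5 or 0.6 (not in the documents). In outcome SDs, the expected 95% half-width is

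t(0.975, df) × c4(df) × √(2/21) × factor,

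where c4 converts the SD to the expected value of its estimate and √(2/21) = 0.3086.

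- Week-4 t-test: df = 40, factor 1, so 2.0211 × 0.9938 × 0.3086 = 0.620.
- Change-score t-test: df = 40, factor √(2(1 − ρ)).
- ANCOVA: df = 39, factor √(1 − ρ²) × 1.0129. The last number is the mean of √(1 + F(1,40)/40), the average cost of chance baseline imbalance. At ρ = 0 this is 2.0227 × 0.9936 × 0.3086 × 1.0129 = 0.628.

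| ρ | Week-4 t-test | Change-score t-test | ANCOVA | ANCOVA ÷ week-4 |
|---|---|---|---|---|
| 0 | 0.620 | 0.877 | 0.628 | 1.014 |
| 0.3 | 0.620 | 0.733 | 0.599 | 0.967 |
| 0.5 | 0.620 | 0.620 | 0.544 | 0.878 |
| 0.6 | 0.620 | 0.554 | 0.503 | 0.811 |

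ANCOVA is narrower than the change-score test in every row, and narrower than the week-4 test from 0.3 upwards.

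**3. Power, as an illustration only.** The value d = 0.784 is borrowed from the defecation count, because no other effect size is documented. Noncentral t, ANCOVA averaged over chance imbalance:

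| ρ | Week-4, two-sided | Change, two-sided | ANCOVA, two-sided | Week-4, one-sided | Change, one-sided | ANCOVA, one-sided |
|---|---|---|---|---|---|---|
| 0 | 0.698 | 0.418 | 0.687 | 0.803 | 0.548 | 0.794 |
| 0.3 | 0.698 | 0.554 | 0.727 | 0.803 | 0.679 | 0.826 |
| 0.5 | 0.698 | 0.698 | 0.806 | 0.803 | 0.803 | 0.885 |
| 0.6 | 0.698 | 0.791 | 0.864 | 0.803 | 0.874 | 0.924 |

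Two-sided, ANCOVA breaks even with the week-4 test at ρ of about 0.16 (0.160 to 0.163 for d from 0.5 to 0.9). To match ANCOVA's two-sided power at ρ = 0.3, 0.5 and 0.6, the week-4 test would need 22.4, 26.9 and 31.4 patients per arm.

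**4. Simulation check.** In 20,000 runs ANCOVA gave half-widths of 0.628, 0.600, 0.544 and 0.502, two-sided power of 0.684, 0.725, 0.804 and 0.863, and a type I error of 0.050 to 0.052.

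**The case against.** The strongest reply is that nothing here is an error. The t-test is valid under randomisation, and on the plan's own one-sided terms it reaches the intended 80% power. Four further points can be made.

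- The correlation is unknown for every outcome. Across the assumed range the effect runs from a slight loss, through a gain worth about one patient per arm at 0.3, to a useful gain at 0.5 and 0.6.
- The comparator is unstated. If the t-test is on change scores, the baseline is already used, and at 0.6 the gain is 9% (0.503 against 0.554), not 19%.
- The power figures borrow the effect size of an outcome that may have no baseline to adjust for.
- On the document's dates the adjustment would come after the analysis, and with no primary outcome named a second model adds analytic choices.

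All four are fair as limits. They make this an improvement with a gain that cannot be fixed in advance. They do not remove the case for it. The interval widths need no borrowed effect size, the loss at zero correlation is small, and ANCOVA does better than either form of the t-test at 0.3 and above. The timing affects how the result must be labelled, and it means that the benefit of pre-specification may already be lost.

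**Conclusion.** The concern holds as a matter of precision, not of bias or validity. For the outcomes with a baseline in Table 1, ANCOVA would change the expected interval width relative to a week-4 t-test by +1.4%, −3%, −12% and −19% at correlations of 0, 0.3, 0.5 and 0.6. At 0.5 that is worth about six patients per arm (26.9 against 21) in the borrowed-effect illustration. The downside near zero correlation is about 0.01 of power.

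These figures assume 21 analysed patients per arm, equal SDs at both times and a linear relation. The correlations are assumed, so confidence in the size of the gain is moderate. The change should be made, but the trial's conclusions do not become invalid without it. No gain is established for the bowel-movement count, because a baseline for it is not clearly planned.

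**What to change.** For each continuous outcome with a baseline entry in Table 1, state the time point and estimate taVNS minus sham by ANCOVA with terms for treatment and that outcome's own baseline, reported with a 95% confidence interval. Week 4 is suggested because it is the only post-baseline time shared by all Table 1 outcomes. Include BSFS only if it is analysed as a mean score, since the scale is ordinal, and blood only for named analytes.

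Base efficacy statements on this contrast and report the within-arm paired changes as descriptive. That is a safeguard, since the plan does not say otherwise. For the bowel-movement count, adjust only if a pre-treatment diary week was recorded; if not, keep the unadjusted between-arm test and say so.

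The cost is one paragraph in the plan and minor analysis work, with no new data for the Table 1 outcomes. Timing is the main constraint. The Timeline section lists "August 2020-October 2020: Data analysis" and the title page reads "Document Date: 5/25/2022". If the analysis has been done, report the adjusted estimate beside the planned t-test and label it as specified afterwards. A pre-treatment diary week that was not recorded cannot now be added.
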